Nonalcoholic hepatic steatosis (NAFLD), now also referred to as MAFLD (hepatic steatosis associated with metabolic dysfunction), is considered the hepatic manifestation of the metabolic syndrome and is currently the most frequent chronic hepatopathy in pediatric age in Western countries (5). Recent studies suggest that fructose consumption is implicated in the development of NAFLD both directly by providing metabolites that can be used for the synthesis of triglycerides and free fatty acids and indirectly through increased uric acid production. In the liver, in fact, fructose is rapidly converted by the enzyme phosphofructokinase C (PKF-C) to fructose-1-phosphate (FP). The depletion of phosphoric groups through the consumption of adenosine triphosphate (ATP) results in the enhanced activity of adenosine deaminase, which converts adenosine monophosphate (AMP) to inosine monophosphate (AMP) which is ultimately converted to uric acid. Finally, uric acid promotes the expression of enzymes involved in lipogenesis, thereby worsening hepatic steatosis (6,7).

In addition, consumption of foods high in fructose could be a risk factor for bone loss (8). Numerous studies conducted over the past 25 years, a period in which fructose use has increased exponentially, have shown that this sweetener tends to increase the incidence of fractures and osteoarthritis and decrease bone mineral density (BMD) and the apposition of new bone tissue (9,10). Fructose would act at the intestinal level by altering calcium and phosphorus absorption mechanisms. Intestinal absorption of calcium is mediated by the active form of vitamin D, 1,25-OH vitamin D, obtained by renal hydroxylation of 25OH-vitamin D. When the body's calcium reserves are sufficient, excess fructose does not have any effect on intestinal absorption; under conditions of reduced dietary intake or increased requirement, such as occurs in developmental age, there is a compensatory increase in circulating levels of 1,25-OH vitamin D in order to increase intestinal absorption and reduce renal excretion of calcium (11). Excess fructose

would appear to act directly at the renal level by reducing the activity of 1α-hydroxylase and increasing the activity of 24-hydroxylase, leading to reduced production of 1,25-OH vitamin D and consequently reduced availability of calcium essential for the apposition of new bone tissue (12).

Reduced phosphate uptake, on the other hand, depends on the depletion of phosphate groups by a specific isoform of phosphofructokinase expressed by enterocytes (13); therefore, the reduction in the ATP/AMP ratio leads to inhibition of the Na/P transporter. This mechanism would also occur at the renal level where inhibition of this transporter promotes urinary excretion of phosphorus (14).

Recent studies show how an increase in dietary fructose appears to be responsible for the onset of several obesity-associated diseases; foremost among them NAFLD, which is increasing in tandem with obesity even in the pediatric population. The aim of this study is mainly to understand the effect of fructose on the molecular events contributing to pediatric development, as this could be an important target to address the clinical and social problems arising from its prevalence in pediatric age.

AIMS OF THE STUDY

The primary aim of this study is to evaluate the effects of fructose intake in a group of preschool children and overweight or obese adolescents; in particular, to investigate the impact of fructose consumption in the development of liver complications, such as NAFLD, and its degree of severity, as well as its impact in other obesity-associated diseases. **In addition, the present study aims to describe the composition of bone metabolism according to the level of fructose consumption.** Secondly, by means of omics analysis (metabolomics and metaproteomic), the aim is to characterize the microorganisms present in the gastrointestinal tract and their microbial activity in relation to dietary habits, fructose intake and clinical parameters. Finally, sociodemographic and cultural factors, in the children and adolescents considered in the study, and in their families, will be surveyed.

STUDY DESIGN

This study consists of two parts, the first phase involves the conduct of a cross-sectional study to assess the relationship between fructose consumption and the presence of NAFLD and the difference in several parameters, including anamnestic, clinical, auxological and hematochemical assays and the presence of the disease, and a second prospective part for the sociological evaluation one year after entering the study. It constitutes an extension of a study already approved by the University of Bari, approval of which is attached by the Independent Ethics Committee university hospital company "Consorziale Policlinico" with approval number CE/7331. The study involves the collaboration of three different units, respectively formed by the University of Eastern Piedmont (unit 1), University of Bari "A. Moro" (unit 2) and the University of Rome "Foro Italico" (unit 3). The first two units will enroll subjects with criteria of interest for the study. The University of Rome, on the other hand, will be concerned with the socioeconomic aspect of the study with the preparation of ad hoc questionnaires to be submitted to both children/adolescents and families.

Subjects

100 overweight or obese preschool children and adolescents visited at the Outpatient Clinic of Pediatric Endocrinology of the AOU Maggiore della Carità in Novara, at the Transition Endocrinology Outpatient Clinic of the SCDU Endocrinology and at the Outpatient Clinic of Pediatric Endocrinology "B.Trambusti" of the Giovanni XXIII Pediatric Hospital in Bari will be included in the study. Subjects will be selected continuously with adherence to the inclusion criteria from January 2024 until the end of December.

Inclusion criteria

- Children and adolescents with expression of informed consent according to art.2 quinque of Legislative Decree n.196/2003;
- Preschool children of both sexes aged 3 to 6 years and adolescents of both sexes aged 12 to 16 years;
- Children diagnosed with overweight (defined by BMI > 97th percentile for children younger than 5 years; and BMI > 85th percentile for children older than 5 years) or obesity (defined by BMI > 99th percentile for children younger than 5 years; and BMI > 97th percentile for children older than 5 years) (15,16).

Exclusion criteria

- Children and adolescents who are not in this age group;
- Children and adolescents with liver disease different than NAFLD;
- Children and adolescents with genetic type obesity or secondary obesity;
- Children and adolescents with skeletal fragility due to genetic causes;
- Children and adolescents who chronically use drugs capable of altering lipid metabolism and bone remodeling;
- Children and adolescents placed on a diet-therapeutic regimen with dietary styles other than the Mediterranean or Western diet (e.g., ketogenic diet, FoodMap diet, vegan/vegetarian diet) to avoid bias in the interpretation of the microbial signature (the microbial signature of the Western and Mediterranean diets is known in the literature);
- Failure of parents or adolescent (from age 12 years) to give informed consent;

Surgery

No type of surgery

DURATION OF THE STUDY

12-month recruitment and 12-month observation period for sociological survey.

SCDU di Endocrinologia

AOU Maggiore della Carità, [name]

[contact] (Reparto); [contact]

[contact]

Timing of data collection

At the time of recruitment, patients afferent at the Outpatient Endocrinology Clinic of the AOU Maggiore della Carità in Novara, at the Transition Endocrinology Outpatient Clinic of the Endocrinology SCDU, and at the "B. Trambusti" Pediatric Endocrinology Outpatient Clinic of the Giovanni XXIII Children's Hospital will undergo:

Questionnaires to assess the amount of fructose introduced in the diet:

- Questionnaire to assess adherence to the Mediterranean diet in children/adolescents, KIDMED;
- Questionnaire to assess food frequency in children, IDEFICS;
- 24h recall questionnaire, to collect information regarding meals taken in the previous 24 hours. The amount of macronutrients will be obtained through dedicated software "Dietosystem Professional Food Therapy Software" from DSMedica. The questionnaire is added with specific questions and figures to identify the portions of foods and put them in relation to the amount of fructose intake;
- Calculation of the Dietary Inflammatory Index (DII) using a list of foods. This parameter makes it possible to define the extent to which a dietary pattern is able to promote the synthesis of pro-inflammatory molecules (17,18);
- Sociological questionnaire prepared ad hoc by Unit 3 to assess diet and fructose intake in relation to family socioeconomic status.

Anamnestic evaluation

- The patient's mother will be asked about the gestational age, mode of delivery and anthropometric data of the child at birth.
- Detection of current drug therapy (if any).

Instrumental assessment

- Quantitative and qualitative analysis of bone composition using quantitative ultrasonography (QUS). This instrument provides different parameters related to bone composition, specifically speed of sound (SOS) assessing bone density, broadband ultrasound attenuation (BUA) assessing trabecular structure, ultrasound peak amplitude assessing trabecular size, number of peaks assessing connectivity of the mineralized matrix structure, and fast wave energy and amplitude assessing elasticity.
- US ultrasound of the abdomen to evaluate hepatic steatosis, perivisceral and subcutaneous fat. The presence of hepatic steatosis (NAFLD) will be classified from stage 1 to stage 3 according to literature (19).

Clinic-auxological evaluation

- Anthropometric measurements, such as weight, height and BMI assessment according to STANDARD DEVIATION SCORE (SDS). Waist and hip circumference measurements.
- Measurement of blood pressure and heart rate.
- Analysis of body composition by bio-impedance analysis (BIA)

Laboratory evaluation, hematochemical assays

Subjects will undergo the following assessments after at least 12 hours of overnight fasting:

- OGTT (glucose-loading curve; glucose 1.75 g/kg per os at time 0', maximum dose 75 g), with basal and every 30 min blood glucose and insulin draws.
- Basal blood draw for c-peptide, AST, ALT, gamma-GT, fractional and total bilirubin, azotemia, creatinine, eGFR, HbAic, fructosamine, total cholesterol, HDL, triglycerides, TSH, FT3 and FT4, leptin, adiponectin, DPP4, uric acid.
- Basal blood sampling for PCR, advanced glycation products (AGEs), AGE receptor (RAGE) and advanced protein oxidation products (AOPPs),
- Basal blood sampling for assay of intermediate products of fructose metabolism (fructose-lysine)
- Calcium, phosphorus, 25-OH vitamin D, PTH, osteocalcin, RANKL, osteoprotegerin, bone isoenzyme alkaline phosphatase, telopeptide C-terminal collagen type I (CTX), intact procollagen amino terminal type 1 (P1NP), IL-6, IL-1beta, biochemical parameters needed to assess bone metabolism.

They will, in addition, be performed:

- A urinalysis and 24-hour urine collection for evaluation of fructose metabolites in urine.
- Fecal sample for metabolomics and metaproteomic analysis.

ANALYSIS BY BIOCHEMICAL, HORMONAL AND MASS SPECTROMETRY PARAMETERS

Biochemical parameters according to clinical practice will be analyzed at the laboratories of Maggiore della Carità Hospital in Novara and at the laboratories of Giovanni XXIII Children's Hospital in Bari by estimation with Siemens Advia 2400 Healthcare Diagnostics, Siemens ADVIA chemistry XPT and in accordance with the respective protocols of reagent use.

Metaproteomic and metabolomics analysis will be conducted on stool, plasma and urine samples stored during the study for omics signature designation. Metaproteomic analysis with UPHLC-MS/MS mass spectrophotometer will be performed on stool samples to identify the presence of microorganisms in the gastrointestinal tract to be then correlated with the diet followed and clinical parameters of the patients. Peptides identified by the analysis will be entered into the UniProtKB, KEGG database and used for phylogenetic analysis.

Metabolomic analysis will be carried out on all three types of samples; metabolomics conducted on fecal samples will allow assessment of the functional activity of microorganisms, characterizing the intermediate phenotype that mediates host-microbiome interactions. Using one-dimensional gas chromatograph coupled with mass spectrometer (GC-MS-SPME), the metabolic profile and changes in metabolite levels in association with fructose intake will be identified. The identification of the main SCFAs will be carried out with the same instrument and then confirmed by injecting the appropriately treated samples into the instrument, comparing the retention time and the corresponding spectra obtained from GC-MS analysis. This method allows a metabolomic signature to be defined in relation to fructose consumption.

SAMPLE SIZE AND STATISTICAL METHODS

The study plans to enroll 100 children afferent to the centers previously listed. Given a first-type error of 0.05, a power of 80%, a variance of equal fructose consumption in the groups of children with and without NAFLD of 9.53 (pooled variance obtained from data reported in the article by Nier et al. (20), a ratio of 1:3 between children with and without NAFLD (expected prevalence in overweight and obese children ~24% (21)), the sample size will allow to highlight as statistically significant a minimal difference in the averages of fructose consumption between healthy and diseased children of 2.02 grams.

Statistical analysis

Evaluation of the relationship between fructose and NAFLD

Descriptive statistics will be calculated in order to summarize the sociodemographic, perceptual, anthropometric, dietary, clinic-auxological, anamnestic and laboratory characteristics of the children included in the study.

Categorical variables will be summarized by absolute frequencies and percentages while numerical variables as mean and standard deviation (SD) or median and interquartile range (Q1-Q3) if not normally distributed according to the Shapiro Wilks test and quantile plot observation. The chi-square test or the corresponding nonparametric Fisher's test will be used to test the association between categorical variables and the presence of NAFLD while the t-test or the Mann-Whitney test will be used to test the difference in fructose consumption between children with NAFLD and those without the disease as well as the presence of differences between the two groups for the other numerical variables. The positive false discovery rate method will be used to account for the presence of multiple tests. Based on the number of NAFLD events observed, stratified analysis by age group (preschool age vs. adolescents) and center will be evaluated. **Regarding the assessment of bone metabolism, mean and standard deviation (SD) or median and interquartile range (Q1-Q3) of the parameters provided by the QUS overall and separately for high and low fructose consumption (below vs above median consumption) will be calculated.**

Microbiota analysis

Initially, an exploratory analysis of the relative abundance of the genera of bacteria in the microbiota will be carried out. The relative abundance of each species detected in the fecal samples will be represented by heatmaps. Next, a beta-diversity analysis will be performed comparing the complexity of genera

between subjects. Specifically, three matrices will be created based on weighted and unweighted Bray-Curtis and Unifrac distances that will be used to perform a principal coordinate analysis to highlight the presence of subject clusters based on the complexity of their microbiota.

The “Linear discriminant analysis effect size” (LEFSE) method will be used to identify taxa that best discriminate between NAFLD-infected and non-infected patients. The LefSE method is an algorithm-based approach that performs the nonparametric Kruskal-Wallis and Wilcoxon rank-sum test to identify bacterial taxa whose relative abundance is statistically different between groups. Then discriminant analysis is applied considering only those bacterial taxa found to be significantly different between the two groups.

EXPECTED RESULTS

The present study is expected to gain new knowledge on the effect of fructose in relation to the onset of obesity-associated liver disease (NAFLD) and bone metabolism, with the identification of new biological, immunological, and omics markers that can be studied in the future as disease targets in the pediatric population. In addition, due to the scientific and sociological interest, the present study aims at the identification of sociodemographic and cultural determinants related to fructose intake, useful for the creation of preventive campaigns aimed at the promotion of a healthy lifestyle, with a change in eating habits that incentivize a healthy diet and a reduction of obesity status in the population. The results obtained, if statistically significant, will ultimately aim to develop effective preventive communication to promote a healthier lifestyle and diet in the population.

ETHICAL ASPECTS

The study was designed and will be conducted in accordance with international and national ethical standards on biomedical research with human beings, specifically:

- *Ethical principles for medical research involving human subjects* (Declaration of Helsinki -World Medical Association, current version);
- European Union *Standards of Good Clinical Practice* (ICH/GCP);
- *Convention on Human Rights and Biomedicine* (Oviedo Convention of 04/04/1997);
- Italian codes of ethics for health professions and specific current national regulations on clinical trials.

Management of informed consent

An information sheet explaining the type of study, purpose, procedures, sample and data collection, and possible benefits and risks of the research is available. This information will be presented to interested persons, who will have the freedom to give consent or to be able to withdraw it when the study has already begun.

Management of sensitive data

The following European and national regulations are kept in mind:

- *Regulation (EU) 2016/679 of the European Parliament and of the Council of April 27, 2016 and subsequent amendments published in the Official Journal of the European Union 127 of May 23, 2018 (GDPR);*
- *Legislative Decree No. 196 of June 30, 2003 (Personal Data Protection Code), as amended by Legislative Decree No. 101 of August 10, 2018 on "Provisions for the adaptation of national legislation to the provisions of Regulation (EU) 2016/679."*
- Art.8 of Legislative Decree 101/2018 of September 19, 2018, for the processing of data in minors under the age of 16, for the expression of informed consent. The Legislative Decree harmonizes the Privacy Code (d.gls. 196/2003) with the EU Regulation 2016/679.

Before the start, the study will be registered on ClinicalTrail.gov and AEA RCT Registry.

DATA PROCESSING METHODS AND BIOLOGICAL SAMPLES

The study involves the collection of information related to lifestyles and diseases of the subjects involved. The biological samples and the attached personal/sensitive data collected will be immediately pseudonymized by random assignment of alphanumeric codes associated with the study and will be entered into the REDCap Management Software. The decoding of said alphanumeric codes will be in the possession of the responsible research investigator. Therefore, it will only be possible for the responsible research investigator to link the information and data obtained from the searches to a specific subject. Personal data will be processed for the purposes set out in the project, in accordance with the principles of lawfulness, fairness, transparency, purpose limitation, minimization and accuracy of data (Art. 5 GDPR) in paper and electronic form by individuals authorized to process the data. Data availability, management, access, storage and usability is guaranteed by the adoption of technical and organizational measures to ensure adequate levels of security (Articles 25 and 32 GDPR). Only researchers involved in the study and authorized by the responsible research investigator will have access to the data.

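### The fructose–NAFLD comparison is unadjusted, so it cannot separate fructose intake from degree of obesity or age; the entry BMI floor, which changes at age 5, adds to this inside the preschool group

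*Combined protocol and SAP*

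**What the plan says.** The inclusion criteria admit two age bands: "Preschool children of both sexes aged 3 to 6 years and adolescents of both sexes aged 12 to 16 years". They define "overweight (defined by BMI > 97th percentile for children younger than 5 years; and BMI > 85th percentile for children older than 5 years" and "obesity (defined by BMI > 99th percentile for children younger than 5 years; and BMI > 97th percentile for children older than 5 years". Both sets of cut-offs therefore apply within the preschool band, while every adolescent falls under the older-age rule.

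The section on clinic-auxological evaluation collects "Anthropometric measurements, such as weight, height and BMI assessment according to STANDARD DEVIATION SCORE (SDS", together with waist and hip circumference. It does not name the reference for the SDS.

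The statistical analysis section, under the relationship between fructose and NAFLD, states that "the t-test or the Mann-Whitney test will be used to test the difference in fructose consumption between children with NAFLD" and those without. The same tests are applied to the "presence of differences between the two groups for the other numerical variables". The only control for age or site is that, depending on the number of NAFLD events, "stratified analysis by age group (preschool age vs. adolescents) and center will be evaluated". No regression, covariate, BMI stratum or split at age 5 is planned for this comparison.

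**The concern.** The Aims section asks what impact fructose has on the development and severity of NAFLD, and the background says that NAFLD is rising together with obesity. A two-group test of intake answers a narrower question. If heavier or older children have more NAFLD and also eat different amounts of fructose, the crude difference contains those links as well as any effect of fructose.

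The entry rule ties one of these factors to age. Below age 5 a child needs a BMI above the 97th percentile to enter; above age 5 the 85th is enough. Within the preschool stratum the minimum degree of excess weight therefore drops at age 5, and intake in grams may well change with age. Analysing preschool children separately from adolescents leaves this step in place.

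At stake is whether a positive, or a null, main result can be read as being about fructose.

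**Working it through.** **1. The plan's own figure.** Inputs from the sample size section: variance 9.53, ratio 1:3, N = 100 (25 and 75), error 0.05 (taken as two-sided), power 80%.
- SD = √9.53 = 3.087 g. Standard error = 3.087 × √(1/25 + 1/75) = 0.713 g.
- Normal approximation: (1.960 + 0.842) × 0.713 = 2.00 g. Noncentral t: 2.017 g, power 80.1% at 2.02 g.
- The stated 2.02 g reproduces, so the sample-size arithmetic is not at issue.

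**2. The step in the entry floor.** The normal quantiles are z(0.97) = 1.88 and z(0.85) = 1.04, a step of 0.84 SDS. The resulting gap in mean BMI-SDS depends on who attends. For a source population with mean μ and SD 1 (assumed), the mean above a floor c is μ + φ(c−μ)/[1−Φ(c−μ)]:

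| Assumed μ | Mean SDS under 5 | Mean SDS over 5 | Gap |
|---|---|---|---|
| 0 | 2.27 | 1.55 | 0.71 |
| 1 | 2.43 | 1.82 | 0.61 |
| 1.5 | 2.56 | 2.03 | 0.53 |
| 2 | 2.72 | 2.30 | 0.42 |
| 3 | 3.25 | 3.06 | 0.19 |

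**3. Leaving out degree of obesity, whole sample.** Simulation with N = 100, no true fructose effect, SD 3.09 g and prevalence 24% (expected figure in the plan). BMI-SDS has an assumed SD of 0.7. The bias is approximately (standardised BMI-SDS difference between NAFLD groups) × (fructose/BMI-SDS correlation) × 3.087.
- Odds ratio 2 per SDS, correlation 0.2: 0.46 × 0.2 × 3.087 = 0.28 g; false positives about 7%.
- Odds ratio 3 per SDS, correlation 0.3: 0.68 × 0.3 × 3.087 = 0.63 g; false positives about 14%.
- Repeated runs over these settings give about 0.3 to 0.65 g and 6 to 14%. With BMI-SDS in the model the false-positive rate is about 5%.
- If either link is zero, there is no bias.

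**4. The entry rule alone, preschool group.** Large-sample simulation with ages uniform from 3, NAFLD odds ratio 2 to 3 per SDS, prevalence 24%, μ from 0 to 1.5 and no age effect on NAFLD (all assumed except the prevalence).
- Children with NAFLD are 0.16 to 0.36 years younger if the band runs to the seventh birthday, and 0.10 to 0.23 years younger if it ends at the sixth.
- At an assumed 1 to 2 g per year of age, the extremes are −0.10 × 1 = −0.1 g and −0.36 × 2 = −0.7 g. For μ of 2 to 3 the bias is smaller.

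**5. Which covariates.** Preschool case with μ = 1, odds ratio 3 per SDS, band to the seventh birthday, intake rising 1 or 2 g per year:

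| NAFLD odds ratio per year of age (assumed) | Crude bias (g) | BMI-SDS only (g) | Age and BMI-SDS (g) |
|---|---|---|---|
| 1.0 | about −0.3 / −0.6 | about 0.04 / 0.08 | about 0 |
| 1.3 | about 0.03 / 0.06 | about 0.33 / 0.65 | about 0 |

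BMI-SDS without age can therefore do worse than the crude test. The two together do not.

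**The case against.** Age-specific cut-offs are not an error: the protocol cites separate growth references for younger and older children. BMI-SDS is not ignored either, since as one of the other numerical variables it would be compared between the NAFLD groups. Every odds ratio, correlation and gram-per-year figure above is assumed, the two mechanisms can have opposite signs, and BMI may lie on the path from fructose to NAFLD. With about 25 expected cases there is little room for covariates.

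Much of this stands. Eligibility need not change, and neither the net size nor the direction of bias can be known from the documents. But displaying a BMI-SDS imbalance does not correct the fructose difference, and two pre-specified covariates are feasible at N = 100. Possible mediation is a reason to show both results, not to omit the adjusted one.

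A reader might infer that younger preschool children are the more obese ones by rule. The documents do not support that: the rule fixes only a minimum, and recruitment is from endocrinology outpatient clinics, where many children may lie well above it. A reader might also infer that the overweight/obese class will mix two definitions in the analysis, but the analysis section names no such variable.

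**Conclusion.** The concern holds as a gap in the analysis. The main comparison cannot separate fructose from degree of obesity or age, and the planned stratification does not deal with the step at age 5.

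The size is conditional: about 0.3 to 0.65 g with 6 to 14% false positives from omitted adiposity, and roughly −0.1 to −0.7 g in the preschool group from the entry rule, each under the assumptions listed. Both are modest against the 2.02 g detectable difference. It is tempting to say that the entry rule could hide or reverse the association, but a bias of at most 0.7 g cannot reverse a true difference of 2.02 g; that reading could apply only to small true differences. The case rests mainly on the general lack of adjustment, with the cut-off step as a contributing reason.

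**What to change.** In the statistical analysis section, pre-specify a linear model of fructose intake on NAFLD status with continuous age and continuous BMI-SDS together, and report it beside the crude comparison. Use the same two covariates within each age stratum if the stratified analysis goes ahead. Do not adjust for BMI-SDS without age. State which growth reference gives the SDS at each age.

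The cost is a few lines of text, since both covariates are already available. Precision falls slightly: holding the residual variance at 9.53, the detectable difference becomes 2.02/√(1−ρ²), which is 2.03, 2.06, 2.12 or 2.20 g for an assumed NAFLD/BMI-SDS correlation ρ of 0.1, 0.2, 0.3 or 0.4. Adding age replaces ρ² by the squared multiple correlation of NAFLD with both covariates, while any variance in intake that they explain works the other way. If BMI lies on the path from fructose to NAFLD, the adjusted figure shows only the part not passing through BMI, so the text should say how the two results are to be read together.

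### Dietary advice given before entry, and steatosis already known, are not recorded, so the cross-sectional fructose–NAFLD difference may partly reflect advice and cannot support claims about development or onset

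*Combined protocol and SAP*

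**What the plan says.** **Who enters.** Subjects are "100 overweight or obese preschool children and adolescents visited at the Outpatient Clinic of Pediatric Endocrinology" and at two other endocrinology clinics in Novara and Bari. Nothing limits entry to first visits or to children not yet advised on diet. The only dietary exclusion covers those "placed on a diet-therapeutic regimen with dietary styles other than the Mediterranean or Western diet". Its stated reason is interpretation of the microbial signature; the fructose exposure is not mentioned.

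**What is measured and when.** Timing of data collection places the diet questionnaires, including a recall of the previous 24 hours, at recruitment. The abdominal ultrasound that classifies steatosis belongs to the same set of assessments. The history items are birth data and current drug therapy. KIDMED scores adherence to a Mediterranean diet, not whether that diet was prescribed.

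**How it is analysed.** Under Statistical analysis, fructose consumption is compared between children with and without NAFLD by t-test or Mann-Whitney test. Stratification by age group and center will be considered, depending on the number of NAFLD cases. No adjustment is described.

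**What is claimed.** Study Design describes a cross-sectional look at a relationship with the presence of NAFLD, and the only prospective part is sociological. The Aims, however, propose "to investigate the impact of fructose consumption in the development of liver complications", and Expected Results anticipates knowledge on "the effect of fructose in relation to the onset of obesity-associated liver disease".

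**The concern.** In a clinic population, current intake can be a consequence of earlier care. A child who has been advised to change diet reports the diet after that advice. If such advice is unevenly distributed between the NAFLD and non-NAFLD groups, the comparison mixes any relation between fructose and the liver with the result of the advice.

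The plan could not detect this. It collects no variable that identifies advised children or shows whether steatosis was known before the diet was recorded. A null or inverse result would then have two explanations that the data could not separate, and a positive result could be understated.

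The wording adds to the problem. Exposure and disease are measured once and together, and no later clinical follow-up is planned. The design therefore cannot show that intake preceded disease, yet the aim and expected results speak of development and onset.

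**Working it through.** **1. The plan's own figure.** Inputs from Sample Size and Statistical Methods:
- "The study plans to enroll 100 children afferent to the centers previously listed";
- "a ratio of 1:3 between children with and without NAFLD", hence 25 and 75;
- "a variance of equal fructose consumption in the groups of children with and without NAFLD of 9.53", hence SD = √9.53 = 3.087 g;
- alpha 0.05 (taken as two-sided; the plan does not say) and power 80%.

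Standard error of the difference = 3.087 × √(1/25 + 1/75) = 0.713 g.

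Normal approximation: (1.960 + 0.842) × 0.713 = 2.00 g. Noncentral t with 98 degrees of freedom: 2.017 g, which rounds to the stated 2.02 g. Power at 2.02 g is 80.1%. The plan's figure reproduces and is not in dispute.

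**2. The bias.** Let p be the share of a group that was advised and r the mean reduction in fructose intake per advised child.

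Net bias B = p(NAFLD) × r(NAFLD) − p(no NAFLD) × r(no NAFLD)

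Observed difference = true difference − B

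If p and r are the same in both groups, B = 0. The documents give neither p nor r for either group, so every value below is an assumption. With r equal in both groups, B = (difference in p) × r.

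**3. Illustration.** True difference 2.02 g, 25 v 75, variance held at 9.53, two-sided noncentral t:

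| Assumed inputs | B (g) | Observed difference (g) | Power |
|---|---|---|---|
| Equal advice and effect | 0 | 2.02 | 80% |
| 20 points more advice, 2 g | 0.4 | 1.62 | 61% |
| 40 points more advice, 2 g | 0.8 | 1.22 | 40% |
| 20 points more advice, 5 g | 1.0 | 1.02 | 29% |

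The sign reverses only if B exceeds 2.02 g.

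**4. Limit of the illustration.** If only some children in a group change their intake, that group's variance rises by p(1 − p)r². With no advised children in the other group, the NAFLD-group variance rises by 0.2 × 0.8 × 2² = 0.64 in the second row, 0.4 × 0.6 × 2² = 0.96 in the third and 0.2 × 0.8 × 5² = 4.0 in the fourth. Holding 9.53 fixed is thus reasonable for the second and third rows and rougher for the fourth.

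**5. What a restricted analysis could deliver.** Suppose half the children had no prior advice, equally in both groups (an assumption), leaving about 12 v 38. Standard error = 3.087 × √(1/12 + 1/38) = 1.022 g. Power for 2.02 g is 49%, and the difference detectable with 80% power is 2.92 g. If advised children are concentrated in the NAFLD group, fewer than 12 might remain there.

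**6. Wording set side by side.** Study Design: cross-sectional, relationship, presence. Aims: impact, development. Expected Results: effect, onset. The last two go beyond the first, and this mismatch needs no numerical assumption.

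**The case against.** The strongest reply is that unequal advice is not shown. All participants are overweight or obese and attend the same kind of clinic, so advice may be given for weight whatever the state of the liver. Steatosis is established for the study by an ultrasound at recruitment, and nothing says that it was known before. Nor do the documents say what a Mediterranean-style regimen does to fructose intake, so even the direction is open. All this stands, and it is why the point is conditional.

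A reader might infer that the design is certain to work against its own hypothesis, or that a bias of about 2 g would wipe out the power. The documents support neither. A 2.0 g bias (40 points × 5 g) does give 5% power at a fixed variance of 9.53. But that scenario would itself raise the NAFLD-group variance to 9.53 + 0.4 × 0.6 × 5² = 15.53, so the figure contradicts its own premise.

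A reader might also infer that applying the exclusion already yields the missing data. It yields only whether a child is on a regimen now, and its style. Past advice, its date and earlier knowledge of steatosis would be new items.

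Finally, the dietary exclusion is deliberate and has a stated microbiota reason, the eligibility of children on a prescribed Mediterranean diet is inferred from its wording, and their number is unknown. The case report form is not among the documents. The causal wording changes no analysis; it does affect what readers will take the results to show.

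**Conclusion.** The point holds as a conditional one. Children on a prescribed Mediterranean- or Western-style regimen are not excluded, intake and NAFLD are measured together, no listed item identifies prior advice or known steatosis, and the comparison is unadjusted. Whether bias results depends on a difference between groups that the documents do not allow anyone to estimate; it may be zero.

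The table gives a sense of scale only: because the target difference is small, a net bias of 0.4 to 1.0 g would matter. It is not an estimate of this study's bias and leaves the sample size calculation intact. The mismatch between the cross-sectional design and the language of development and onset holds without any assumption.

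The case for acting is that the information is cheap to collect at entry, and without it nobody could later tell which situation applied.

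**What to change.** 1. Add history fields at entry: current or prior dietary regimen or advice (yes/no, with start date), and whether steatosis was already known.
2. Report the share of children advised in each NAFLD group.
3. Pre-specify one sensitivity analysis of the fructose comparison, either adjusted for prior advice or restricted to children without it. Present it beside the main result and label it supportive, since it will be imprecise (about 49% power for 2.02 g if 12 v 38 remain).
4. Reword the primary aim and Expected Results to *association between current fructose intake and presence of NAFLD*, in line with Study Design, and state that the order of exposure and disease cannot be established.

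Cost: a few extra case report form fields, one less precise secondary analysis and a wording change. Eligibility, sample size and the main analysis are unchanged.
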